6.1.3 Other Secondary Endpoints

The following are additional secondary endpoints, evaluated in the AIM-HN part of the study in both the high VAF and all VAF populations:

- Time to response
- Time to progression (TTP)
- Progression-free survival (PFS)
- 6 month and 9 month progression-free survival rate
- Overall survival (OS)
- Overall survival rate at one year
- Changes in measures of quality of life using the following tools: EORTC QLQ-H&N35 and EQ-5D-5L
- Population PK parameters of tipifarnib
- Adverse Events
- Laboratory test results
- Vital Signs
- ECG results

Response and progression endpoints will be analyzed using both IRF and Investigator assessments, as well as using the mITT and per-protocol analysis sets.

6.2 Study Design

KO-TIP-007 is an international, multicenter, open-label, pivotal study, with two non-comparative sub-studies: (1) an interventional open label, single arm, pivotal study evaluating the efficacy of tipifarnib in HRAS mutant HNSCC (AIM-HN) and (2) an observational study to

evaluate the impact of HRAS mutations on response to first line systemic therapies for HNSCC (SEQ-HN).

AIM-HN, includes HNSCC subjects with HRAS mutations. AIM-HN subjects will receive treatment with tipifarnib and the outcome of this sub-study will address the primary objective of the KO-TIP-007 study. SEQ-HN, is an observational sub-study and includes wild type HRAS HNSCC subjects who consent to provide first line outcome data and additional follow up. HNSCC patients in whom HRAS mutations are identified during SEQ participation, and who meet eligibility criteria will be offered participation in AIM-HN. [REDACTED]

[REDACTED]

[REDACTED]

[REDACTED]

[REDACTED]

KO-TIP-007 will enroll a total of at least 305 subjects. AIM-HN, the tipifarnib treatment sub-study of KO-TIP-007, will investigate the efficacy of tipifarnib in at least 80 subjects with head and neck tumors of confirmed squamous histology with HRAS mutations. SEQ-HN, the non-interventional observational sub-study will enroll an additional, at least 225 subjects with HRAS wildtype HNSCC tumors. Additional HRAS mutant subjects that consent to pre-screening, but do not enroll in AIM-HN may have first line treatment data collected as well.

The study design is shown in [Figure 1](#).

6.2.1 AIM-HN Design

AIM-HN will enroll patients with head and neck tumors of confirmed squamous histology with HRAS mutations. Subjects must have failed (e.g. tumor progression, clinical deterioration, or recurrence their most recent prior therapy, and at least one prior line of systemic platinum-based therapy (the most recent prior and platinum-based therapy may be the same regimen). However, subjects who, at the judgment of the investigator, are considered not to be candidates to receive standard therapy with a platinum-containing regimen may also be enrolled (further detailed in [Section 4.6](#)). The primary objective of AIM-HN is to determine the ORR of tipifarnib in subjects with HNSCC with HRAS mutations and a VAF \geq 20%, as assessed by IRF.

To participate in AIM-HN, all subjects must have measurable disease that meets the criteria for selection as a target lesion according to Response Evaluation Criteria in Solid Tumors (RECIST) v1.1. The presence of at least one measurable target lesion per RECIST v1.1 must be confirmed by local radiology prior to enrollment. Subjects without at least one measurable target lesion confirmed by local radiology will not be enrolled into AIM-HN.

HNSCC diagnosis by local site pathology laboratory will be used for study entry; however, all subjects must provide pathology material for central pathology review. Confirmation of pathological diagnosis of HNSCC will be required for inclusion of subjects in the per-protocol

analysis set. Subjects in whom a diagnosis of HNSCC is not confirmed by central review may continue to receive study treatment and will be included in the mITT analysis set.

All AIM-HN enrolled subjects must have a known missense HRAS tumor mutation based on centralized testing or other HRAS test used by the trial site that has been approved by the Sponsor. HRAS status should be assessed on tumor obtained subsequent to the most recent prior therapy in order to obtain the most recent tumor biology; if tumor tissue that does not meet this criterion must be used (e.g. risk of biopsy is too high, patient refuses new biopsy), the Investigator should document the reason. If several samples are available, HRAS testing should be performed in the most recently obtained tumor sample. All subjects must provide enough tumor material for confirmation of HRAS status by central lab. This tissue should be from the same source as that used for pre-screening, or the reason that is not possible documented. Subjects who were enrolled in the study based on HRAS mutation using a Sponsor approved test, but in whom a missense HRAS mutation is not confirmed by central testing, may continue to receive study treatment. SEQ-HN subjects who were initially identified as wild type HRAS but in whom an HRAS mutation is later detected during the course of their standard therapy, will become eligible to enroll in AIM-HN.

AIM-HN enrolled subjects will receive tipifarnib administered at a dose of 600 mg, orally with a meal twice a day (bid) for 7 days in alternating weeks (Days 1-7 and 15-21) in 28-day cycles. Stepwise 300 mg dose reductions to control treatment-related, treatment-emergent toxicities are described in [Section 8.1.2](#). In the absence of unmanageable toxicities, subjects may continue to receive tipifarnib treatment until disease progression. If a complete response is observed, and subject continues to tolerate therapy, therapy with tipifarnib will be maintained for at least 6 months beyond the start of response.

Tumor assessment for the primary analysis will be performed by the IRF according to RECIST v1.1 and assessed by an Independent Data Monitoring Board (IDMB). Investigator assessment of tumor response will also be collected and reported as a supportive analysis. Assessments will be performed at screening and approximately every 8 weeks for the first 12 months of a subject's participation in AIM-HN; thereafter, tumor response assessment should occur approximately every 12 weeks until disease progression. Radiological assessments will be discontinued at the time of tumor progression. If the subject initiates a new anticancer therapy without evidence of disease progression by RECIST v1.1, tumor scans should continue until there is evidence of disease progression unless withdrawal of subject's consent to study procedures. Local investigator evaluation of tumor assessment will guide on-study treatment decisions, including decisions to stop study treatment due to progressive disease.

Upon disease progression, all subjects will be followed approximately every 12 weeks for survival and the use of subsequent therapy until either death or End of Study (up to 2 years since the enrollment of the last study subject in AIM-HN, see [Section 6.7.1](#)), whichever occurs first.

All subjects will be followed-up for safety through the End of Treatment visit which occurs approximately 30 days after treatment discontinuation or until immediately before the administration of another anticancer treatment, whichever occurs first. Additional safety follow-up may be conducted if unresolved toxicity is present at this End of Treatment visit. The IDMB will provide periodic evaluations of safety and other data to ensure adequate benefit/risk as well as the validity and scientific merit of the study.

An overview of the AIM-HN design is shown in [Figure 2](#).

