12.1 Statistical Methods

12.1.1 Efficacy

For the AIM-HN analyses, the estimate of the ORR will be calculated based on the maximum likelihood estimator (i.e., crude proportion of tipifarnib treated subjects whose best overall response is Complete Response (CR) or Partial Response (PR) by IRF) using the mITT analysis population set. Confirmation of response is required. The estimate of the objective response rate will be accompanied by 2-sided 95% exact binomial confidence interval. Efficacy will also be evaluated among the planned 80 subjects in the per-protocol analysis set, as well as summarized based on Investigator assessment of tumor response. [REDACTED]

[REDACTED]

[figure not shown]
Time to objective response (OR) and duration of objective response (DOR) will be calculated for tipifarnib treated subjects who achieve CR or PR. For such subjects, the time to OR is defined as

number of days from enrollment in AIM-HN until start of PR or CR (whichever occurs first), while duration of objective response is defined as the number of days from the start date of PR or CR (whichever response is achieved first) to the first date that progressive disease is objectively documented. Disease progression will be determined by IRF using RECIST v1.1 but local treatment decisions will be made by the Investigator based on local tumor measurements and other clinical information. The duration of objective response will be right-censored for subjects who achieve CR or PR and meet one of the following conditions: 1) non-protocol anticancer treatment started before documentation of disease progression, 2) death or documented disease progression after more than 1 missed disease assessment visit, or 3) alive and does not have documentation of disease progression before a data analysis cutoff date. The analyses will be performed as determined by the IRF using RECIST v1.1. Additional supportive analyses will be conducted using the investigator assessment.

The time to OR and DOR will be summarized descriptively using the Kaplan-Meier method. The 50th percentile of the Kaplan-Meier distribution will be used to estimate the median response duration and a 95% confidence interval for the median response duration will be computed.

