Progression-free survival (PFS) will be defined as the time (in months) from enrollment into AIM-HN to either first observation of progressive disease or occurrence of death due to any cause within 126 days (approximately 2 time intervals for tumor assessments) of either first administration of tipifarnib or the last tumor assessment. In subjects without a progression date or with a death date more than 126 days after the first administration of study drugs or the last tumor assessment, the PFS time should be censored on the date of last tumor assessment or date of first administration of study tipifarnib, whatever occurs last. Progression-free survival analyses should consider tumor assessments after treatment discontinuation or metastatic surgery. Survival will be defined as the time (in months) from enrollment to the occurrence of death due to any cause. Sensitivity analyses for PFS and survival will be performed according to the FDA Guidance for Industry Clinical Trial Endpoints for the Approval of Cancer Drugs and Biologics (May 2007).

Survival and PFS endpoints will be summarized descriptively using the Kaplan-Meier method. The 50th percentile of the Kaplan-Meier distribution will be used to estimate the median PFS and overall survival and 95% confidence intervals for the median response duration will be computed.

[REDACTED]

Descriptive statistics will be primarily used to summarize the demographic data collected in this study. For continuous variables, the number of patients with non-missing data, mean, either the standard error or standard deviation, median, 25th percentile (first quartile), 75th percentile (third quartile), minimum, and maximum will be presented. For discrete data, the frequency and percent distribution will be presented.

Hierarchical testing to adjust for multiplicity will be employed, beginning with the primary objective and working downward until first $p > 0.025$ 1-sided, at which time testing for purposes of firm conclusions will stop.

Sensitivity analyses will be performed to evaluate the robustness of statistical inferences, e.g., to assess the impact of missing data on the conclusions. In addition, a sensitivity analysis will be conducted to evaluate of the impact of the selected VAF cut point on the primary and key secondary analyses, and to determine the VAF cut point which is most predictive of clinical benefit.

[REDACTED]

[REDACTED]

[REDACTED]

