**6 Study Estimands**

Objectives	Estimands
Primary for AIM-HN	
To determine the objective response rate (ORR) of tipifarnib in subjects with Head and Neck Squamous	
 
Population of interest: mITT Analysis Set for subjects with High VAF
 
Variable/endpoint of interest: ORR by IRF
 

[REDACTED]

Sponsor: Kura Oncology, Inc.

Statistical Analysis Plan

Protocol no: KO-TIP-007

Version 1.0 Date: 06-Jun--2023

[figure not shown]
Cell Carcinoma (HNSCC) with HRAS mutations with a VAF $\geq$ 20% (High VAF population), as assessed by Independent Review Facility (IRF)	
Key Secondary for AIM-HN	
To determine the ORR of tipifarnib in subjects with HNSCC with HRAS mutations of any VAF (All VAF population), as assessed by IRF	
 
Population of interest: mITT Analysis Set
 
Variable/endpoint of interest: ORR by IRF
 

To determine the Duration of Response (DOR) of tipifarnib in subjects with HNSCC with HRAS mutations with a VAF $\geq$ 20%, as assessed by IRF	
 
Population of interest: mITT Analysis Set for subjects with High VAF and confirmed objective response (CR or PR)
 
Variable/endpoint of interest: DOR by IRF
 

To determine the DOR of tipifarnib in subjects with HNSCC with HRAS mutations of any VAF, as assessed by IRF	
 
Population of interest: mITT Analysis Set for subjects with confirmed objective response
 
Variable/endpoint of interest: DOR by IRF
 

Other Secondary for AIM-HN	
To determine the anti-tumor activity of tipifarnib in terms of progression free survival (PFS), and rate of PFS at 6 and 9 months in both the high VAF and all VAF populations	
 
Population of interest: mITT Analysis Set for subjects with High VAF/all VAF
 
Variable/endpoint of interest: PFS by IRF including the 6 month and 9 month progression-free rate
 

To determine the anti-tumor activity of tipifarnib in terms of overall survival (OS), and rate of OS at 12 months in both the high VAF and all VAF populations	
 
Population of interest: mITT Analysis Set for subjects with High VAF/all VAF
 
Variable/endpoint of interest: OS including the 12 month OS rate
 

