### 7.3.3 Duration of Response (DOR)

DOR (months) is defined as the time from the date of first response (CR or PR) to the date of progression of disease or death of any cause, whichever occurs first, in patients with a confirmed CR or PR, i.e., (date progression of disease or death – date of first CR or PR + 1)/30.4375.

The censoring rules for DOR is identical to it for PFS as specified in [Table 1](#).

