**Table 1 PFS Censoring Rules**

Hierarchy Censoring	Situation	Date of Event or Censor	Event / Censor
1	No baseline radiological tumor assessment (confirmed measurable disease per RECIST v1.1) available	Treatment start date	Censor
5	No post baseline tumor assessment available and no death reported within 2 scan intervals following treatment start date	Treatment start date	Censor
	No post baseline tumor assessment available but death reported within 2 scan intervals following treatment start date	Date of death	Event
6	No tumor progression and no death reported within 2 scan intervals following last adequate tumor assessment	Date of last adequate assessment	Censor
	No tumor progression but death reported within 2 scan intervals following last adequate tumor assessment	Date of death	Event
	Tumor progression documented within 2 scan intervals following previous adequate tumor assessment	Date of progression	Event
3	Tumor progression documented after 2 scan intervals following previous adequate tumor assessment	Date of previous adequate assessment	Censor
2	New anticancer treatment started and no tumor progression	Date of previous adequate assessment prior to new therapy	Censor
4	No tumor progression and patient lost to follow-up or withdrawal of consent	Date of last adequate assessment	Censor

Notes: Adequate tumor assessment refers to a baseline assessment or a post-baseline assessment with an overall response of CR, PR, SD, non-CR/non-PD, or PD.

If target, non-target, and new lesion assessments have different dates within a visit, then the earliest of those dates will be considered as the date of the tumor assessment if the assessment for that visit is PD; otherwise, the latest date will be used.

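### IRF-based DOR and PFS can be biased upward when the investigator calls progression before the IRF, and no analysis in the readable SAP bounds this

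*Protocol*

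**What the plan says.** **Who ends treatment and imaging.** Protocol 6.2.1 states "Local investigator evaluation of tumor assessment will guide on-study treatment decisions, including decisions to stop study treatment due to progressive disease". The same section states "Radiological assessments will be discontinued at the time of tumor progression", without saying whose progression is meant. Protocol 9.2.7 limits End of Treatment imaging to subjects who stopped for a reason other than death or progression. Protocol 9.2.8 requires follow-up imaging visits only for subjects who stopped for a reason other than progression. Protocol 6.2.1 adds: "If the subject initiates a new anticancer therapy without evidence of disease progression by RECIST v1.1, tumor scans should continue".

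**Who judges the endpoint.** Protocol 12.1.1, on DOR: "Disease progression will be determined by IRF using RECIST v1.1 but local treatment decisions will be made by the Investigator". SAP section 6 gives the PFS variable as "PFS by IRF including the 6 month and 9 month progression-free rate".

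**Censoring.** In SAP Table 1, a subject who starts new treatment without progression is censored (hierarchy 2) at "Date of previous adequate assessment prior to new therapy". A subject with no progression, and no death within two scan intervals of the last adequate assessment, is censored at that assessment (hierarchy 6). A death inside that window is an event. For DOR, SAP 7.3.3 says "The censoring rules for DOR is identical to it for PFS as specified in" Table 1.

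**Supportive analyses.** Protocol 6.1.3 plans response and progression endpoints by both reads. Protocol 12.1.1 adds investigator-based supportive DOR analyses and says "Sensitivity analyses for PFS and survival will be performed according to the FDA Guidance for Industry". SAP 9.7.2 summarizes response-related endpoints by both reads. The only analysis that the readable SAP calls a sensitivity analysis is the per-protocol repeat in 9.7.

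**The concern.** Take a subject whom the investigator calls progressed at a scan that the IRF reads as not progressed. Treatment stops, the subject leaves the scheduled imaging visits, and new therapy may begin. The IRF series then has no progression and no later scan on which to find one, so Table 1 censors the subject at that scan. Kaplan-Meier assumes that a censored subject has the same outlook as those still followed. This subject has just been judged progressed by one reader and is more likely than the others to progress soon. Removing such subjects lowers the estimated hazard and lifts the curve.

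IRF-based DOR, in the High VAF and All VAF populations, makes up two of the three key secondary endpoints. The trial has a single arm, so no control group shares the bias and the absolute curve is the result.

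**Working it through.** **1. The plan's own figures.** The two-scan windows under SAP Table 1 reproduce: 16×7+7 = 119, 16×7+14 = 126, 20×7+14 = 154 and 24×7+14 = 182 days.

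**2. Does investigator progression end imaging?** Section 6.2.1 does not name the assessor. The investigator decides to stop treatment for progression, and 9.2.7 and 9.2.8 schedule no imaging after such a stop. No readable step asks for IRF confirmation before scans end. So the visit schedule, rather than an explicit rule, takes the subject off imaging.

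**3. Model for DOR.** From the documents: scans every 8 weeks, which is Δ = 56/30.4375 = 1.840 months. The 12-weekly schedule after the first year on study is ignored. Assumed, because the documents do not give them: exponential time to investigator progression with median M = 5 months; a share q of investigator progressions that the IRF would call one scan later; no deaths.

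The chance of passing one scan interval without progression is s = 2^(−Δ/M) = 2^(−1.840/5) = 0.7749, so h = 1 − s = 0.2251. After k scans:

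- censored at the investigator's scan: S_cens = [1 − h(1 − q)]^k
- imaging continued to IRF progression: S_cont = s^k + q(s^(k−1) − s^k)

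Three scans fall by 6 months (5.52) and six by 12 months (11.04). For q = 20% and k = 3:

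- S_cens = (1 − 0.2251×0.8)³ = 0.8199³ = 0.551
- S_cont = 0.4653 + 0.2×(0.6005 − 0.4653) = 0.492

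| q | 6-month, censored | 6-month, continued | excess (points) | 12-month, censored | 12-month, continued | excess (points) |
|---|---|---|---|---|---|---|
| 0% | 46.5% | 46.5% | 0 | 21.6% | 21.6% | 0 |
| 10% | 50.7% | 47.9% | 2.8 | 25.7% | 22.3% | 3.4 |
| 20% | 55.1% | 49.2% | 5.9 | 30.4% | 22.9% | 7.5 |
| 30% | 59.8% | 50.6% | 9.2 | 35.7% | 23.5% | 12.2 |

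A simulation of 200,000 responders agrees within rounding. With M = 7 months, the 12-month excess runs from about 3.5 to 12 points.

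**4. PFS.** With M = 6 months, s = 2^(−1.840/6) = 0.8085 and h = 0.1915. At q = 20% the 6-month rate is (1 − 0.1915×0.8)³ = 60.7% when censored, against 0.5285 + 0.2×(0.6537 − 0.5285) = 55.4% with imaging continued. Simulated over medians of 4 to 8 months, the 6-month excess is about 2 to 3 points at q = 10%, 5 to 6 at 20% and 9 to 14 at 40%.

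**5. Deaths inside the window.** Add two further assumptions: a 4-month median survival after progression, and new therapy in half of the discordant subjects. A death within 126 days without new therapy is then an event. For DOR with M = 5 and q = 20%, the simulated excess falls from 5.9 to 4.7 points at 6 months and from 7.4 to 5.4 at 12 months.

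**6. Counting investigator progression as the event.** In the step 3 model this gives s³ = 46.5% at 6 months, against 49.2% with continued imaging at q = 20%. It lies below the target, but close to it.

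**The case against.** A reader might infer from the schedule that the IRF curves are informatively censored. The documents show a risk, not a fact. The stop rule names no assessor, so IRF progression is a possible reading, no discordance rate is given, and the bias is zero if the reads agree.

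A reader might also infer that every discordant subject is censored. Table 1 counts deaths within two scan intervals as events, which weakens the bias as in step 5. It does not remove it, because new therapy ranks above that row and deaths after new therapy appear to be censored too. Continued scanning after new therapy applies only where there is no RECIST progression, and Table 1 censors before new therapy in any case.

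A third tempting reading is that no sensitivity analysis exists. That goes too far. The protocol plans investigator-based DOR and PFS and guidance-based PFS sensitivity analyses. The readable list of changes in SAP section 3 does not drop the last of these, and part of that list and of Protocol 12.1.1 is redacted. What stands is narrower. Investigator-based DOR uses other readers and possibly other responders, so it does not bound the IRF curve. Investigator-based PFS uses the same mITT subjects and escapes this censoring, but it is a separate estimate, and the SAP's both-reads sentence covers response-related endpoints and so does not clearly carry it over. The per-protocol repeat keeps the same censoring rules.

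On materiality, the readable text sets no threshold for DOR, and precision is limited. At the hypothesized 30% ORR, 80 subjects give 24 responders. A rate of 49% then has a 95% half-width of 1.96×√(0.49×0.51/24) ≈ 20 points, ignoring censoring, and 10% to 30% of 24 is only 2 to 7 subjects. That is fair, but a wide interval does not show which way the estimate leans.

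**Conclusion.** The concern holds as a risk of upward bias in IRF-based DOR and PFS that no analysis in the readable SAP bounds. Under the assumptions of step 3 (5-month median, IRF call one scan late in 10% to 30% of responders), the DOR rate is overstated by about 3 to 9 points at 6 months and 3 to 12 at 12 months. These figures are at the upper end for those inputs, because early deaths that count as events reduce them. The absence of a bounding analysis can be claimed only for the unredacted text.

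A reader might extend the point to the primary endpoint. That would be wrong: ORR is a proportion, and follow-up censoring does not enter it.

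**What to change.** In SAP 9.7.2:

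1. Add a sensitivity analysis of IRF DOR and PFS. Subjects with investigator progression and no IRF progression, whose imaging then stops or who start new therapy, count as events on the investigator progression date. Label it a conservative bound.
2. Report how many IRF censorings are of this type, for DOR and for PFS, in High VAF and All VAF subjects. If the number is zero, the concern is closed.
3. Carry the protocol's investigator-based PFS and its PFS sensitivity analyses explicitly into the SAP.

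Both reads and subsequent therapy are already collected, so no new data are needed. The added cost is one analysis that reads less favourably than the main one. Naming the assessor in the imaging stop rule would address the cause, but SAP section 3 refers to the early closure of the study, and scans not taken cannot be recovered. The analytic bound is the practical remedy.
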